#### **Ordinal scales**

a) The absolute value and change from baseline in the Ordinal scale from Day 1 through Day 29 will be summarized by treatment group and visit using descriptive statistics.

Mean change in Ordinal scales through Day 29 will be evaluated by fitting a linear mixedeffects model for repeated measures (MMRM). The model will include change from baseline in Ordinal scale as the repeated dependent variable; treatment (as a class variable), visit (as a class variable), and treatment-by-visit interaction and as fixed effects; baseline Ordinal scale, age and gender as covariates; and measures within subject at each visit as a repeated measure.

An unstructured covariance matrix will be used to model the within-subject error. If the fit of the unstructured covariance structure fails to converge, a compound symmetry covariance structure will be used. Parameters will be estimated using restricted maximum likelihood with the Kenward-Roger method for calculating the denominator degrees of freedom. Data collected at Days 3, 7, 14, and 29 visits will be included in this analysis. Missing data will not be imputed.

From this model, the least-squares (LS) means and 95% CIs for each treatment group, the treatment difference in the LS means, the 95% CI for the difference, and the associated p-value will be reported on Days 3, 7, 14, and 29.

b) The proportion of subjects in each severity category of the 7-point Ordinal scale at Days 1,
 3, 7, 14, and 29 visits will be summarized by treatment group. The difference in severity

category distribution between each C19-IG 20% dose group and placebo at Day 3, Day 7, Day 14, and Day 29 will be examined using proportional-odds cumulative logit model. The cumulative logits model will compare lower ordinal scales to higher ones, or equivalently, less favorable outcomes to more favorable ones. The model may be adjusted for baseline characteristics such as age and gender, if appropriate. The estimated odds ratio and 95% CI will be presented. Graphical illustrations of the fitted model will also be presented for Day 3, Day 7, Day 14, and Day 29.

The proportional odds assumption will be tested using a score test at the two-sided alpha level of 0.05. If the proportional odds assumption is not satisfied, given the anticonservative nature of the score test, the proportional odds model will still be used for the analysis, and the results will be presented along with the score test p-value to help put these results in context. If the proportion odds assumption is rejected or if the proportional odds model fails to converge, a sensitivity or alternative analysis using a non-parametric Wilcoxon Rank Sum test will be performed. The p-value from Wilcoxon Rank Sum test, as well as the Hodges-Lehmann estimate of the treatment difference and the corresponding 95% CI will be provided.

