# 3. INVESTIGATIONAL PLAN

## 3.1 Study Design

This is a prospective, multi-center, randomized (1:1:1), double-blind study of C19-IG 20% at 1 of 2 dose levels versus Placebo in asymptomatic, ambulatory outpatients aged  $\geq$ 18 years who are SARS-CoV-2 positive. Participants will be stratified by age <65 years vs  $\geq$ 65 years of age. The study will enroll asymptomatic subjects with laboratory-confirmed novel coronavirus (SARS-CoV-2) infection as determined by qualitative PCR (reverse transcriptase [RT]-PCR), or other commercial or public health assay approved by regulatory authorities as a diagnostic for COVID-19 (inclusive of SARS-CoV-2 antigen testing or other approved rapid testing platforms) in any specimen obtained  $\leq$  5 days prior to randomized treatment ( $\leq$  5 days is the post-sampling timeframe from date specimen obtained to administration of blinded study drug). Every effort should be made to reduce this time interval to the minimum as nearly immediate treatment is key for successful intervention.

Approximately 801 subjects (267 per arm) will be randomized (1:1:1). Subjects randomized to C19-IG 20% will receive a blinded subcutaneous (SC) infusion on Day 1 at a dose of either 1 gram or 2 grams, according to the randomized dose assigned. Subjects randomized to Placebo will receive a SC infusion of sterile 0.9% sodium chloride injection, United States Pharmacopeia (0.9% NaCl, USP) or equivalent. Blinded study drug will be prepared and administered by an unblinded study nurse who is entirely independent of the evaluating study team with SC infusions using 2 separate syringes as follows:

- Placebo (*two* syringes each containing 5 mL 0.9% NaCl);
- 1 gram C19-IG 20% (one syringe containing 5 mL C19-IG 20% *Plus* one syringe containing 5 mL 0.9% NaCl)
- 2 grams C19-IG 20% (*two* syringes each containing 5 mL C19-IG 20%).

An independent DSMB will review interim safety data when approximately 399 patients have been randomized and treated with follow-up through Day 29 (approximately 133 patients per randomized group).

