# 4. GENERAL CONSIDERATIONS FOR DATA ANALYSIS

Unless otherwise specified, continuous variables will be summarized using descriptive statistics (n, mean, standard deviation, median, minimum, and maximum). Categorical variables will be summarized showing the number and percentage of subjects within each category.

Summary results will be provided for each treatment group. All tabulations will be based on pooled data across centers.

All statistical tests will be two-sided and tested at the 5% level of significance.

Unscheduled visits will be excluded from the summaries but will be included in the data listings.

All p-values will be displayed to four decimal places, with p-values less than 0.0001 presented as '<0.0001'. Minimum and maximum values will be reported in the units of collection with 3 decimals being maximum value; the mean will be presented with 1 decimal place more and the standard deviation 2 decimal places more than the units of collection. Percentages for categorical summaries will be represented to 1 decimal place.

Analyses will be performed using SAS for Windows statistical software, version 9.4 or higher (SAS, Cary, NC), except where other software may be deemed more appropriate. In the event that other software is used to perform some analyses, the details will be provided in the Clinical Study Report.

will perform all efficacy and safety analyses described in this SAP and Grifols will review them.

Subject data will be listed, sorted by treatment group and subject number. When applicable, listings will be additionally sorted by visit and assessment date/time.

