#### 4.5 Multiple Comparisons

A hierarchical ordered testing procedure will be employed for handling the multiplicity issue to maintain the overall family-wised alpha level at 0.05 for comparisons between each dose and placebo. The null hypothesis for 1g vs placebo is tested only if the superiority for the 2g dose compared to placebo has been shown at a two-sided significance level of 5%. The order in which the null hypotheses are tested for the primary endpoint is predetermined as below:

- 1. Ho1: no difference between 2g and placebo on primary efficacy endpoint
- 2. Ho2: no difference between 1g and placebo on primary efficacy endpoint

The primary efficacy analysis will be carried out on the mITT population and repeated on the ITT and PP population (if different from the mITT population).

There will be no adjustment for multiple comparisons on secondary and exploratory efficacy endpoints.

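### If the unstructured MMRM for the ordinal scale or NEWS fails to converge, the compound-symmetry fallback misstates visit-specific standard errors, too small at some visits and too large at others

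*SAP*

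**What the plan says.** SAP 6.2, under *Ordinal scales*, models change from baseline with treatment, visit and their interaction, adjusted for baseline score, age and gender. On the covariance: "An unstructured covariance matrix will be used to model the within-subject error". The only alternative offered is: "If the fit of the unstructured covariance structure fails to converge, a compound symmetry covariance structure will be used". On inference: "Parameters will be estimated using restricted maximum likelihood with the Kenward-Roger method for calculating the denominator degrees of freedom". No empirical standard error is named. On the data: "Data collected at Days 3, 7, 14, and 29 visits will be included in this analysis", and "Missing data will not be imputed".

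The NEWS analysis, under *Assessment of clinical severity* in the same section, repeats this specification. For both endpoints the treatment difference, its 95% CI and its p-value are reported separately at Days 3, 7, 14 and 29.

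SAP 4 sets the test level: "All statistical tests will be two-sided and tested at the 5% level of significance". SAP 4.5 adds: "There will be no adjustment for multiple comparisons on secondary and exploratory efficacy endpoints". SAP 9 places both endpoints in the futility package, analyses them by the Section 6.2 methods, and plans no sensitivity analysis at that look.

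**The concern.** An unstructured covariance has a separate variance for each visit. Compound symmetry has one, shared by all four. Moving from the first straight to the second discards exactly what a visit-by-visit confidence interval depends on. Kenward-Roger does not repair this, because it takes the chosen structure as correct.

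Unequal variances are the natural expectation. Protocol 5.1 admits only asymptomatic outpatients with NEWS of 2 or less, so ordinal scores start near the top of the scale. Some subjects then fall ill: SAP 10 assumes 20% of placebo subjects are no longer asymptomatic at Day 14 (100% − 80%). Equal variance at all four visits is the one pattern under which compound symmetry does no harm, and nothing in the documents supports it.

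At stake is the reading of nominal, unadjusted p-values. The ordinal scale has a second, per-visit proportional-odds analysis that does not use this matrix. NEWS has no other inferential analysis.

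**Working it through.** **Inputs from the documents.** Four visits; two-sided 5% level; three equal arms of 267. The 267 is about 240 evaluable with 10% withdrawal: 240/0.9 = 266.7. The plan states no standard error, variance or correlation for the ordinal scale or NEWS, so there is no planned figure to reproduce. The only SD given is 1.5 log10, for viral load.

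**Formula.** Let v_j be the variance of the change score at visit j, and v̄ the mean of the four. With complete data, equal arms and a full treatment-by-visit mean, the compound-symmetry variance estimate is v̄. Then

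- SE under compound symmetry = √(2v̄/n); correct SE at visit j = √(2v_j/n)
- ratio r_j = √(v̄/v_j)
- true size of a nominal 5% test = 2[1 − Φ(1.96 r_j)]

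**Worked case, variances 1:3:3:1.** v̄ = 8/4 = 2. Days 7 and 14: r = √(2/3) = 0.816, size 11.0%. Days 3 and 29: r = √2 = 1.414, size 0.6%.

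**Range.** All patterns are assumptions. Entries are the true size in %.

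| Assumed pattern, Days 3/7/14/29 | Day 3 | Day 7 | Day 14 | Day 29 |
|---|---|---|---|---|
| Equal variances | 5.0 | 5.0 | 5.0 | 5.0 |
| Variances 1:1.5:1.5:1 | 2.8 | 7.4 | 7.4 | 2.8 |
| SDs 0.5/0.7/0.7/0.5 | 1.7 | 8.9 | 8.9 | 1.7 |
| SDs 0.3/1.0/1.0/0.5 | <0.1 | 13.4 | 13.4 | 0.3 |
| SDs 0.2/0.6/0.8/0.3 | <0.1 | 8.3 | 19.3 | 0.1 |
| Variances 1:4:2:1 | 0.6 | 16.6 | 5.0 | 0.6 |
| Variances 0.3:1:1:1 | 0.1 | 7.5 | 7.5 | 7.5 |
| Variances 0.5:1:1.5:2 | 0.2 | 2.8 | 7.4 | 12.1 |
| Variances 1:2:3:6 | 0.1 | 1.6 | 5.0 | 16.6 |

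The last two rows, where variance rises to Day 29, reverse the direction at Day 7.

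**Ordinal-score illustration.** Assume everyone starts at 7. The assumed shares are 5% at score 6 on Day 3; 15%, 1% and 1% at scores 6, 5 and 4 on Day 7; 12%, 1% and 2% on Day 14; and 3% at score 6 on Day 29. With no deaths, the Day 7 and Day 14 ratios are 0.80 and 0.72 (size 11.6% and 16.0%). Death scores 1 and is permanent. Adding deaths of 0.5%, 1% or 2% by Day 29 (0.1%, 0.2% or 0.8% by Day 14) moves the Day 7 ratio to 0.93, 1.04 and 1.28. The Day 14 ratio becomes 0.79, 0.84 and 0.84.

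**Check by simulation.** Compound-symmetry REML fits used 3 × 240 subjects, 10% monotone dropout and an assumed correlation of 0.5.

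- Variances 1:3:3:1 (250 replicates): the model SE was about 0.13 at every visit, against empirical SEs of 0.093/0.167/0.165/0.099. Rejection was 0.4/11.6/11.2/0.8%.
- Variances 1:2:3:6 (200 replicates): rejection was 0/3.0/9.0/19.5%.
- Equal variances (150 replicates): SE ratios were 0.94 to 0.99.

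Monte Carlo error on the rejection rates is about 2 to 3 points.

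**How often the fallback is reached.** Unstructured REML fits were run on simulated ordinal data with the same sample size and dropout, and correlations of 0.5 and 0.8 (200 replicates each, a purpose-written routine rather than SAS).

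| SDs, Days 3/7/14/29 (about) | Converged, correlation 0.5 | Converged, correlation 0.8 |
|---|---|---|
| 0.24/0.48/0.48/0.22 | 200/200 | 200/200 |
| 0.11/0.37/0.44/0.14 | 199/200 | 199/200 |
| 0.05/0.38/0.44/0.11 | 167/200 | 166/200 |

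In the last row only about 2 of 720 subjects are below the top score at Day 3.

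**The case against.** The strongest reply is that the fallback will rarely be used. The planned analysis is unstructured, with 4 × 5/2 = 10 covariance parameters and about 800 subjects, and unequal variances alone do not break such a fit. In the simulations above, failure became common only when Day 3 variance was almost nil. This stands: the error rates are conditional on an event whose probability the documents do not allow one to state. They are therefore a reason to mend the rule, not a forecast.

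Near-zero variance is also less plausible for NEWS. Baseline may be 0 to 2, and Protocol Appendix 2 awards points for ordinary variation in heart rate, blood pressure, saturation or temperature, so some spread exists at every visit. This stands too. Against it, NEWS has no second inferential analysis to expose a wrong standard error if the fallback is reached.

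A third reply is that heterogeneous structures must estimate the same near-zero variance and may fail with it. That is correct, and it decides how the list of fallbacks should end.

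Finally, these are secondary endpoints without confirmatory alpha, and the only formula at the interim is conditional power for the primary endpoint. That limits the consequence but does not remove it. SAP 9 also rests the futility decision on an assessment of the secondary outcomes, with fewer subjects than at the end, so non-convergence is more plausible there.

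**Conclusion.** The fallback is a weak rule. If reached, it misstates the standard error at any visit whose variance departs from the four-visit average. Under the assumed patterns, the true error of a nominal 5% test is roughly 7 to 19% at high-variance visits and below 3% at low-variance visits.

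A reader might infer that the variances must differ, that the Day 7 and Day 14 standard errors will always be too small, or that the fallback is likely. The documents support none of these. They give no visit variance for either endpoint. The Day 7 error reverses if variance rises to Day 29, as it may on the ordinal scale, where death is permanent and scores lowest. Non-convergence looks unlikely unless one visit has almost no variance. Nor does the point reach the primary chi-square test, the dose hierarchy or the sample size.

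The change is still worth making, because it is cheap and works whichever way the error runs.

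**What to change.** In both places in SAP 6.2, replace the single fallback with an ordered list: heterogeneous Toeplitz, then heterogeneous AR(1), then heterogeneous compound symmetry, taking the first that converges. Use the empirical (sandwich) standard error for any structure other than unstructured, and limit the Kenward-Roger sentence to the unstructured fit. Because a near-zero variance at one visit may break the heterogeneous structures as well, name a last step that does not depend on estimating it within a joint model. This can be compound symmetry with the sandwich error, or a per-visit ANCOVA with a robust error. Choose one in advance, and state that the same list applies at the futility look.

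The cost is about one sentence in each of two sections. Kenward-Roger is given up where the sandwich error is used, which is minor at about 240 per arm. A per-visit ANCOVA does not use a subject's other visits when one is missing. The sandwich error corrects the standard error only; with missing data the estimate still depends somewhat on the working structure, which is why the heterogeneous structures come first.

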### Assessment of clinical severity

The NEWS will be calculated based on 7 clinical parameters and recorded on the eCRF. The absolute value and change from baseline in the total score from Day 1 through Day 29 will be summarized by treatment group and visit using descriptive statistics.

Change in NEWS total score through Day 29 will be evaluated by fitting a linear mixed-effects model for repeated measures (MMRM). The model will include change from baseline in NEWS total score as the repeated dependent variable; treatment (as a class variable), visit (as a class variable), and treatment-by-visit interaction as fixed effects; baseline NEWS total score, age and gender as covariates; and measures within subject at each visit as a repeated measure.

An unstructured covariance matrix will be used to model the within-subject error. If the fit of the unstructured covariance structure fails to converge, a compound symmetry covariance structure will be used. Parameters will be estimated using restricted maximum likelihood with the Kenward-Roger method for calculating the denominator degrees of freedom. Data collected at Days 3, 7, 14, and 29 visits will be included in this analysis. Missing data will not be imputed.

From this model, the least-squares (LS) means and 95% CIs for each treatment group, the treatment difference in the LS means, the 95% CI for the difference, and the associated p-value will be reported for Day 3, Day 7, Day 14, and Day 29.

### Proportion of subjects requiring at least one COVID-19 related medically attended visit through Day 29

The proportion of subjects requiring at least one COVID-19 related medically attended visit for management/treatment of COVID-19 (apart from routinely scheduled study-directed visits) within each treatment group will be presented along with a two-sided exact (Clopper-Pearson) 95% CI.

The observed difference in the proportion of subjects requiring at least one COVID-19 related medically attended visit between each C19-IG 20% dose group and placebo along with the exact unconditional 95% CI for risk difference will be calculated. The null hypothesis will be tested using Chi-square statistic and the p-value will be reported.

A listing of all medically attended visit data collected through the study will be provided.

### Proportion of subjects requiring hospital admission through Day 29

The proportion of subjects requiring hospital admission through Day 29 within each treatment group will be presented along with a two-sided exact (Clopper-Pearson) 95% CI.

The observed difference in the proportion of subjects requiring hospital admission between each C19-IG 20% dose group and placebo along with the exact unconditional 95% CI for risk difference will be calculated. The null hypothesis will be tested using Chi-square statistic and the p-value will be reported.

### **Duration of Hospitalization through Day 29**

The duration (number of days) of hospitalization from post-randomization through Day 29 will be calculated based on hospital admission and discharge dates recorded on the eCRF. Number of days in the hospital will be compared between each C19-IG 20% dose group and placebo using an ANCOVA model, including number of days in the hospital as a dependent variable, treatment group as a fixed effect, and baseline characteristics such as age and gender as covariates. From this model, the LS means and 95% CIs for each treatment group, the treatment difference in the LS means, the 95% CI for the difference, and the associated p-value will be presented.

In the event the data is highly skewed, e.g. very few subjects hospitalized, a sensitivity analysis using a non-parametric Wilcoxon Rank Sum test will be performed. The p-value from Wilcoxon Rank Sum test, as wells as the Hodges-Lehmann estimate of the treatment difference and the corresponding 95% CI will be provided.

Subjects who died while in the hospital will be assigned as in the hospital for the number of days remaining from the day of death to Day 29 for the analysis. Subjects who were in the hospital at study completion will be assigned a hospitalization end date equals to the date of completion for the purpose of deriving the duration of hospitalization. Subjects who never been hospitalized through Day 29 will be included in the analysis with a value of zero days in the hospital.

#### Proportion of subjects requiring ICU admission through Day 29

The proportion of subjects requiring ICU admission through Day 29 within each treatment group will be presented along with a two-sided exact (Clopper-Pearson) 95% CI.

The observed difference in the proportion of subjects requiring ICU admission between each C19-IG 20% dose group and placebo along with the exact unconditional 95% CI for risk difference will be calculated. The null hypothesis will be tested using Chi-square statistic and the p-value will be reported.

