#### 7.2.3 Day 3 Healthcare Provider Visit

Assessments include the following:

- Ordinal Scale assessment
- NEWS (Appendix 2)
- Surveillance for COVID-19 symptoms (detailed checklist) including: fever, cough, shortness of breath, fatigue, myalgia etc.
- Vital signs (temperature, systolic and diastolic blood pressure, pulse, respiratory rate)
- Record oxygen saturation (specify on or off oxygen supplementation)
- Record any Medically Attended Visit(s) for management/treatment of COVID-19 (other than routine study-directed visits) in any setting, specifying type (eg, Emergency department, urgent care, outpatient clinic/professional setting for direct inperson/telemedicine medical assessment and care of COVID-19 provided by licensed healthcare personnel)
- If subject requires supplemental oxygen post randomization: Record any supplemental oxygen administration (type, %, flow start/end date/time)
- If subject requires hospital admission post randomization: Record hospital admission and discharge dates
- If subject requires ICU admission post randomization: Record ICU admission and discharge dates
- If subject requires invasive mechanical ventilation post randomization: Record details of invasive mechanical ventilation parameters (start/end date/time)
- Respiratory sample for quantitative measurement of SARS-CoV-2 viral load by NAT or PCR (real-time RT-PCR) (obtained via nasopharyngeal swab)
- Record SAEs and TEAEs
- Record concomitant medications

	Number	BIG-CL-PRT-000028	Version	2.0	Status	Effective	Effective Date	13-Oct-2021
VILOL2	GC2010 - A	Multicenter, Randomized, Double-blind,	, Parallel Gro	up Study to E	aluate the Saf	ety and Efficacy of		3013-02
and Colored	Anti-COVID-19 Immune G	lobulin (Human) 20% (C1	19-1G 20%) ve	rsus Placebo	in Asymptoma	ic Ambulatory	rage	OOL 10 07

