- Proportion of subjects who require ICU admission or initiation of ICU-level care\* through Day 29.
- If admitted to ICU post randomization: Duration of ICU stay through Day 29.
- Proportion of subjects requiring invasive mechanical ventilation through Day 29.
- If requiring invasive mechanical ventilation post randomization: Duration of invasive mechanical ventilation through Day 29
- All-cause mortality through Day 29.
- Incidence of critical COVID-19 illness, defined as any one of the following: (a) requiring ICU admission or ICU level of care\*, (b) invasive mechanical ventilation, or (c) resulting in death by Day 29.
- Length of time to clinical progression to critical COVID-19 illness through Day 29 (defined as the time to death, invasive mechanical ventilation, or ICU admission/requiring ICU level of care).
- Time to COVID-19 symptoms specifically defined as the time to fulfillment of the case definition used for the primary efficacy variable through Day 14.

[\*Note: ICU level care is defined as the medical need for intensive or invasive monitoring; immediate or impending need for the support of the airway, breathing, or circulation; and/or stabilization of acute severe or life-threatening complications of COVID-19]

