#### **Duration of ICU stay through Day 29**

The duration (number of days) of ICU stay from post-randomization through Day 29 will be calculated based on ICU admission and discharge dates recorded on the eCRF. Number of days in the ICU will be compared between each C19-IG 20% dose group and placebo using an ANCOVA model, including number of days in the ICU as a dependent variable, treatment group as a fixed effect, and baseline characteristics such as age and gender as covariates. From this model, the LS means and 95% CIs for each treatment group, the treatment difference in the LS

means, the 95% CI for the difference, and the associated p-value will be presented.

In the event the data is highly skewed, e.g. very few subjects admitted to ICU, a sensitivity analysis using a non-parametric Wilcoxon Rank Sum test will be performed. The p-value from Wilcoxon Rank Sum test, as wells as the Hodges-Lehmann estimate of the treatment difference and the corresponding 95% CI will be provided.

Subjects who died while in the ICU will be assigned as in the ICU for the number of days remaining from the day of death to Day 29 for the analysis. Subjects who were at ICU at study completion will be assigned an ICU end date equals to the date of completion for the purpose of deriving the number of ICU days. Subjects who never been in the ICU through Day 29 will be included in the analysis with a value of zero days in the ICU.

#### Proportion of subjects requiring invasive mechanical ventilation through Day 29

The proportion of subjects requiring invasive mechanical ventilation through Day 29 within each treatment group will be presented along with a two-sided exact (Clopper-Pearson) 95% CI.

The observed difference in the proportion of subjects requiring invasive mechanical ventilation between each C19-IG 20% dose group and placebo along with the exact unconditional 95% CI for risk difference will be calculated. The null hypothesis will be tested using Chi-square statistic and the p-value will be reported.

#### Duration of invasive mechanical ventilation through Day 29

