The observed difference in the mortality rate (proportion of deceased subjects) between each C19-IG 20% dose group and placebo along with the exact unconditional 95% CI for risk difference will be calculated. The null hypothesis will be tested using Chi-square statistic and the p-value will be reported.

Subject status after Day 29 (vital status [living or deceased], any hospital admissions, ICU admissions, requirement for invasive mechanical ventilation, need for oxygen supplementation) collected at Day 60/Final Phone Check visit will be presented in a listing.

#### Proportion of subjects with critical COVID-19 illness through Day 29

Critical COVID-19 illness is defined as any of the following: (a) requiring ICU admission or ICU level of care, (b) invasive mechanical ventilation, or (c) resulting in death by Day 29.

The proportion of subjects with critical COVID-19 illness defined above within each treatment group will be presented along with a two-sided exact (Clopper-Pearson) 95% CI.

The observed difference in the proportion of subjects with critical COVID-19 illness between each C19-IG 20% dose group and placebo along with the exact unconditional 95% CI for risk difference will be calculated. The null hypothesis will be tested using Chi-square statistic and the p-value will be reported.

#### Time to clinical progression (critical COVID-19 illness) through Day 29

Clinical progression is defined as death, start of invasive mechanical ventilation, or ICU admission/requiring ICU level of care through Day 29, whichever occurs first. The time to clinical progression will be estimated using the KM method. The KM estimates along with 95% CI, and survival curves will be provided. Based on the KM estimates, the probabilities of experiencing clinical progression and associated 95% CIs on Days 14 and 29 will be reported; in addition, the 25%, 50% (median), and 75% percentiles of the time to clinical progression with associated 95% CIs will be provided, as data permit. The survival rates between each C19-IG 20% dose group and placebo will be compared using Log-rank test. The p-value from Log-rank test will be presented.

#### Time to COVID-19 symptoms through Day 14

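### The ICU proportion is defined to include ICU-level care, but SAP Section 6.2 analyses ICU admission only, and no documented item records ICU-level care given outside an ICU

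*SAP*

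**What the plan says.** **Definition.** SAP Section 2.2.2 lists the endpoint as "Proportion of subjects who require ICU admission or initiation of ICU-level care" through Day 29. Protocol Sections 4.1.2 and 7.1.2 use the same definition, and it reappears in the interim lists of Protocol Section 9.3 and SAP Section 9. A note explains the second half by need rather than by place: "ICU level care is defined as the medical need for intensive or invasive monitoring", among other criteria.

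**Analysis.** Under the heading for the ICU proportion, SAP Section 6.2 states "The proportion of subjects requiring ICU admission through Day 29 within each treatment group will be presented", and the treatment comparison follows suit: "The observed difference in the proportion of subjects requiring ICU admission between each" dose group and placebo.

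**Related endpoints.** In the same section, the critical-illness proportion has as its first component "requiring ICU admission or ICU level of care". Time to clinical progression also includes ICU level of care, and the event-date rule in SAP Section 4.6 calls for the date of admission or of requiring such care.

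**Collection.** The Day 3 visit list (Protocol Section 7.2.3) reads "If subject requires ICU admission post randomization: Record ICU admission and" discharge dates. The lists in Sections 7.2.4 to 7.2.9 and the schedules in Protocol Appendix 1 and SAP Appendix A ask for the same dates and nothing more about intensive care.

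**The concern.** The endpoint has two halves, and the analysis text uses one. Because the definition turns on medical need, it takes in subjects who meet it without entering an ICU. Section 6.2 as written leaves them out of the ICU proportion.

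The two critical-illness endpoints name the missing half but rely on information that the documented collection does not request. Two tables meant to describe the same severe course could then disagree, and a component of a composite could be empty because nobody asked for it rather than because it did not occur.

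Severe events will be few in subjects who are asymptomatic at entry, so each one matters to how these endpoints read. All three are also on the list of secondary outcomes that the unblinded team assesses at the futility review.

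**Working it through.** This is mainly a comparison of texts. The plan gives no expected rate for the endpoint, so there is no figure to reproduce.

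**Step 1: follow three kinds of subject through the rules as written.**

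- *Admitted to an ICU.* An event in the ICU proportion and in critical illness, dated by the admission date. No problem.
- *ICU-level care outside an ICU, then invasive ventilation or death.* A non-event in the ICU proportion under Section 6.2. An event in critical illness through the ventilation or death component, both of which are recorded. The progression date is the ventilation start or the death, which may fall after ICU-level care began.
- *ICU-level care outside an ICU, with neither ventilation nor death.* A non-event in the ICU proportion. By definition an event in critical illness, but no listed item says that it happened or when. If it goes unidentified, the subject is a non-case in the proportion, and SAP Section 4.4 censors the subject at last contact on or before Day 29 in the time analysis.

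The third kind of subject is the gap that runs through all three endpoints.

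**Step 2: check whether ICU duration has the same fault.** SAP Section 2.2.2 defines it as "If admitted to ICU post randomization: Duration of ICU stay through Day 29". Section 6.2 has it "calculated based on ICU admission and discharge dates recorded on the eCRF". Definition and analysis agree, so it does not.

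**Step 3: gauge the scale.** Inputs:

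- 20% symptomatic on placebo, that is 100% minus the 80% assumed to stay asymptomatic (Protocol Section 9.2, SAP Section 10).
- 5% of people with COVID-19 admitted to an ICU (Protocol Section 2). This is a general figure, not one for this population.
- 267 subjects per arm.

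Expected ICU admissions per arm at the placebo rate: 0.20 x 0.05 x 267 = 2.67, or 2.67 / 267 = 1.0%.

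The 5% counts admissions, so subjects treated outside an ICU are additional to the 2.67. If a share f of all ICU-level care is given outside an ICU, the additional number is 2.67 x f / (1 - f). The documents give no value for f. Taking 10% to 40% purely as an assumption:

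- f = 10%: 2.67 x 0.10 / 0.90 = 0.30 per arm, total 2.97 (1.1%).
- f = 40%: 2.67 x 0.40 / 0.60 = 1.78 per arm, total 4.45 (1.7%).

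These are subjects missed by the ICU proportion. The number missed in critical illness is smaller, because those who are ventilated or die are still counted there.

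**The case against.** The best defence is that Section 6.2 is shorthand. SAP Section 9 restates the full endpoint and then says the interim outcomes are analysed by the methods of Sections 6.1 and 6.2, which suggests that the authors meant the method to serve the full definition. Section 6.2 abbreviates elsewhere too: its hospital-admission analysis drops the qualifier that excludes quarantine stays. This is plausible, but it does not settle the matter. The same section spells out ICU level of care for critical illness and progression, and even the generous reading leaves the full endpoint without a documented data source.

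A second defence is that other records help. Oxygen type and flow, ventilation times, hospital dates, the ordinal scale and concomitant medications are all collected, and SAP Section 6.2 mentions a Respiratory Support eCRF. These would capture some airway and breathing support. However, no rule maps them to ICU-level care, and the definition also covers intensive monitoring and circulatory support.

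The eCRF itself is not among the documents. The page that SAP Section 6.2 names for oxygen and ventilation refers to ICU admission in its title, but a title does not show every field. A reader might infer that the item is certainly absent or that the component can never be derived. The documents show only that it is not specified.

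It is also fair to say that these are secondary endpoints without multiplicity adjustment (SAP Section 4.5) and that few events are expected.

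**Conclusion.** The inconsistency stands. The ICU proportion is defined with two components and analysed with one. The second component, which the critical-illness proportion and time to progression also need, has no documented item or date. The consequence is limited to subjects with ICU-level care outside an ICU. Those with neither invasive ventilation nor death are the ones at risk of being lost from all three endpoints.

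The number is unknown and probably small. About 2.7 ICU admissions per arm is an illustration resting on a general COVID-19 rate, and the 0.3 to 1.8 additional subjects rest on an assumed share. The textual finding depends on neither. The primary analysis, the sample size and the conditional power for the primary endpoint are untouched. The futility decision also weighs the secondary outcomes, so the endpoints should be consistent before that review.

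Four stronger readings are tempting and are not supported:

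- That ICU days are also mis-analysed. They are defined for admitted subjects only, and the analysis matches.
- That critical illness outside an ICU cannot be dated at all. Ventilation and death are recorded and dated.
- That missed subjects should be subtracted from the 2.7. That figure is already an admission count.
- That the definition was written to allow for full ICUs. The documents give no reason for it.

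**What to change.** In SAP Section 6.2, use the Section 2.2.2 definition (admission or initiation of ICU-level care) in the heading, the proportion and the treatment comparison for the ICU proportion.

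Check the eCRF. If it does not already capture ICU-level care, add a yes/no field and a start date to the existing ICU item, and reflect this in Protocol Sections 7.2.3 to 7.2.9, Protocol Appendix 1 and SAP Appendix A. The ICU proportion, the critical-illness proportion and the progression date in SAP Section 4.6 should then draw on that one variable. Leave the analysis of duration of ICU stay as it is.

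The cost is a SAP wording change, a small eCRF and protocol edit if the field is missing, and some queries for subjects already hospitalised. It should be settled before the unblinded interim output is reviewed.
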